Title	A double-blinded, prospective, randomized, controlled trial comparing dexamethasone versus ketorolac injection for the treatment of local inflammatory hand and upper extremity disorders: a pilot study		
Short Title	Ketorolac in hand and upper extremity soft tissue disorders		
Protocol Number	Pending		
Phase	Phase 3		
Methodology	Randomize, double-blind, prospective active control trial		
Study Duration	2 – 3 years		
Study Center(s)	Single-center – NYU Langone Medical Center		
Objectives	The primary objective of this study is to compare local corticosteroid hand and elbow injections to placebo or ketorolac to determine if there is an equal or better reduction of symptoms for common orthopaedic upper extremity disorders including: De Quervain's tenosynovitis, trigger fingers, and tennis elbow (lateral epicondylitis).		
Number of Subjects	Goal of 780 total subjects: • 260 subjects in each of the 3 treatment groups (De Quervain's tenosynovitis, trigger fingers and lateral epicondylitis)		
Diagnosis and Main Inclusion Criteria	Subjects 18 years or older, with any of the following diagnoses: De Quervain's tenosynovitis, trigger fingers, or lateral epicondylitis		
Study Product, Dose, Route, Regimen	Peritendonous soft tissue injection for De Quervain's tenosynovitis, trigger fingers and lateral epicondylitis: • 1 mL of ketorolac (30mg/mL) and 0.5 mL (5mg) of 1% lidocaine		
Duration of administration	Single administration, with a second injection permitted only once as subject desires due to no major clinical response at the 4 or 8-week follow-up.		
Reference therapy	Standard of care peritendonous soft tissue injection for De Quervain's tenosynovitis, trigger fingers, and lateral epicondylitis: • 1 mL of dexamethasone sodium phosphate (4mg/mL) and 0.5 mL (5mg) of 1% lidocaine		
Statistical Methodology	The sample size as stated above was derived by a power analysis. A power analysis indicated that a total sample size of 200 patients randomized equally (1:1 randomization) to each treatment arm (i.e trigger finger, De Quervain's disease, and tennis elbow) without any blocking or stratification would provide 80% statistical power (alpha=.05, beta=0.20) to detect a 10% difference in mean DASH scores between cohorts assuming a common standard deviation of 25% (effect size = 10/25 = 0.4). To account for an estimated 30% loss to follow-up, we plan to enroll a total of 260 patients per treatment arm (i.e. trigger finger, De Quervain's disease, and tennis elbow). In total, there will be approximately 780 patients enrolled among all treatment arms.		

1 Introduction

This document is a protocol for a human research study. This study is to be conducted in accordance with US government research regulations, and applicable international standards of Good Clinical Practice, and institutional research policies and procedures.

1.1 Background

Many orthopaedic hand disorders are comprised of different forms of tendonitis, tenosynovitis, and arthritis. The inflammatory processes of these disorders cause discomfort and functional impairment for patients. Decreasing the inflammatory response by use of splinting, physiotherapy, systemic anti-inflammatory agents, and local anti-inflammatory injections helps to alleviate some or all of the discomfort (2-4). Steroid injections are not entirely benign, and complications include tendon ruptures, subcutaneous fat atrophy, skin pigmentation changes, cartilage damage, and hyperglycemic responses in diabetics (9-11, 22-23). Studies have shown that ketorolac, a non-steroidal anti-inflammatory agent has a potent anti-inflammatory effect comparable to corticosteroids and a strong analgesic effect allowing for reduced opioid consumption postoperatively (7, 8). One could argue that the potent anti-inflammatory properties of ketorolac could be used to substitute for local corticosteroid injections in treating certain hand disorders. Given the side-effect profile for corticosteroids it may be beneficial to treat inflammatory disorders with local ketorolac injections. Nonsteroidal anti-inflammatory agents also have their known systemic adverse effects including gastric ulceration and intestinal bleeding as well as impairment of renal function. Most of these side effects are theoretically avoided with local tissue injections.

1.2 Study Drugs

Ketorolac

The proposed use of ketorolac in this study is outside of the FDA-approved indication and is the investigational agent in this study

Ketorolac is a non-steroidal anti-inflammatory drug (NSAID). The approved indication for Ketorolac is for the short-term (≤5 days) management of moderately severe, acute pain that requires analgesia at the opioid level, usually in a postoperative setting. It is highly protein bound (99%) and is largely metabolized by the liver. In it's approved indication it is contraindicated for those with renal impairment, active peptic ulcer disease, pregnant or nursing females, individuals with NSAID hypersensitivity, or individuals at high risk for bleeding/clotting disorders.

Dexamethasone

Dexamethasone is a synthetic corticosteroid and possesses glucocorticoid activity, and will be used within its labeled indication for this study: intra-articular or soft tissue injection for: synovitis of osteoarthritis, epicondylitis, acute nonspecific tenosynovitis. It is the active comparator in this study.

In its approved indication there use limitations for immunocompromised individuals, pregnant females, persons with allergy to steroids, individuals with systemic fungal infections, and individuals with cerebral malaria. It is contra-indicated in systemic fungal infections, and hypersensitivity to any component of this product, including sulfites.

Lidocaine

Lidocaine is a local anesthetic of the amide type, and will be used within its labeled indication for this study: production of local or regional anesthesia by infiltration techniques such as percutaneous injection. It is to be given as concomitant therapy with both the investigational agent, ketorolac injection, and the standard of care therapy, dexamethasone injection.

1.3 Preclinical Data

There are no published studies in the literature that examine local injections of ketorolac in treating orthopaedic hand pathology. Shapiro et al investigated the effects of local injection of corticosteroid and ketorolac on histologic and biomechanical properties of rabbit tendon and cartilage (1). Their goal was to determine the safety and efficacy of local injection of NSAIDs in humans by first testing the histologic and

biomechanical properties of tissues injected with NSAIDs versus corticosteroids in rabbit models. Among the results obtained the study showed that methylprednisolone compared to ketorolac demonstrated a significant increase in cartilage necrosis which was not seen at all in the ketorolac group. The damaging effects of corticosteroids on cartilage has been studied in the literature and it is well known that it is detrimental to cartilage if overused (13, 14). The Shapiro study also showed no notable difference in histologic inflammatory cells when comparing the two groups and no evidence of tendon necrosis despite other studies showing evidence for tendon necrosis/rupture with corticosteroid injections. Case reports exist in the literature that report flexor digitorium superficialis and profundus ruptures following corticosteroid injections for trigger fingers (9, 26). In addition, rabbit model studies show that corticosteroid injection into tendons produce necrosis of collagen resulting in incomplete repair and increased risk for rupture of the tendon (12). The Shapiro study concluded that peri-tendinous injections of either corticosteroid or ketorolac may not be harmful, however cartilage seems to show damage with corticosteroid injections alone (1). The Shapiro study shows that ketorolac does not cause any more harm than corticosteroids when analyzing biomechanical and histologic properties in rabbit models and in some cases causes less damage as demonstrated with cartilage.

1.4 Clinical Data to Date

Investigations comparing local injections of corticosteroids and non-steroidal anti-inflammatory drugs (NSAIDs) have been conducted. One study by Karthikeyan et al showed that subacromial injections with corticosteroids outperformed injections with tenoxicam at 2 and 4 weeks post injection (24). More recently, a double-blind randomized study between triamcinolone and ketorolac injections into the subacromial space demonstrated that ketorolac showed greater improvements in shoulder functional scores at 4-weeks of follow-up and therefore was found to have equivalent if not superior efficacy compared to steroids without the potential steroid side-effects such as tissue atrophy or cartilage damage (25).

In addition there are several studies that examine the potent anti-inflammatory effects of ketorolac when compared to corticosteroids in other fields of research. The ophthalmology literature has examined the effect of ketorolac for postoperative inflammatory control following cataract surgery. When comparing it to corticosteroids, ketorolac topical ophthalmic formulations were as effective as corticosteroids in controlling inflammation and pain following cataract surgery without the known complications associated with corticosteroids including infection, increased intra-ocular pressure, and inhibition of cellular wound-healing (6, 8).

1.5 Dose Rationale

Dose rationale for the study was determined based on available concentrations and clinical data. Ketorolac is readily available at very low costs in vials of 15mg/mL and 30mg/mL. The Shapiro study that examined ketorolac injection into rabbit tendon and cartilage showed favorable safe results using 15mg/mL concentrations and the Min study comparing ketorolac to triamcinolone in the shoulder used 60mg of ketorolac (1,25). We chose 30mg/mL concentrations simply because for small injections in the hand and upper extremity this should prove sufficient if any outcome were to be recorded. A lower concentration puts the study at risk for showing no clinical response. Because the side-effect profile is essentially equivalent between the two we chose to proceed using the higher of the two readily available concentrations.

The dose of dexamethasone used in this study is based on the standard of care used on patients for hand and upper extremity pathology which consists 4mg/mL of dexamethasone sodium phosphate per injection.

Lastly, 1% lidocaine is used in this study to provide simple analgesia from the injections for immediate relief for patients as these injections can be painful at times. This is a standard of care dose of local analgesia.

1.6 Research Risks & Benefits

1.6.1 Risk of Study Drug

All patients will be monitored closely as per the data and safety monitoring plan established for this project for any side-effects that may arise from using these medications for local soft tissue infections. Patients will be checked for common side effects at the time of their follow-up visits. In addition, the patient will be given instructions to contact the private office/HJD hand clinic to report any potential side effects that they may be experiencing.

Risks associated with dexamethasone injections include (9-11, 22-23):

- Pain/discomfort at the site of injection
- Tendon ruptures
- Subcutaneous fat atrophy
- Skin pigmentation changes
- Cartilage damage
- Hyperglycemic responses in diabetic patients

Risks associated with Ketorolac in the literature refer mainly to systemic or intramuscular administration and no risks are noted for local soft tissue injections. Ketorolac has been shown to cause (28-29):

- Pain/discomfort at the site of injection
- Increased risk for bleeding
- Skin rashes
- Pruritis
- Allergic reactions such as face/throat swelling
- Abdominal pain/GI upset
- Gastrointestinal ulcers/GI bleeding
- Renal impairment

Risks associated with lidocaine mainly involve side-effects from systemic administration which include (30,31):

- CNS depression or excitation (light-headedness, nervousness, apprehension, euphoria, confusion, dizziness, drowsiness, tinnitus, blurred vision, vomiting, twitching, convulsions, unconsciousness, respiratory depression and arrest)
- Bradycardia
- Hypotension
- Cardiovascular collapse
- Allergic reactions

Protection against risks

Patients will be injected using sterile technique to avoid any infectious risk with the medication. Patient will be informed that some discomfort will be experienced with needle injection however small gauge needles will be used to minimize the pain felt by the patient. Any patient that experiences an adverse event will be withdrawn from the study and will follow-up with their primary care provider promptly.

Payment for the office visit and any procedures performed will be billed to the insurance company of the patient and the patient is responsible for any copayments needed.

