3.2 Primary Study Endpoints

The primary endpoint will be functional outcome scores at various follow-up time points using the quickDASH and EQ-5D questionnaire as well as a pain visual analog scale. The primary endpoint for the study would be resolution of symptoms or surgical intervention.

Primary endpoints will depend on the diagnosis of the patient. The following details what will be assessed at each follow-up visit after the initial injection:

- 1) Trigger finger group primary endpoint measures include the resolution of objective triggering and resolution of tenderness at the A1 pulley at subsequent follow-up visits. In addition, patients will be graded based on the Quinnell system to monitor for improvement: 0-normal movement of finger; 1-uneven movement; 2-active correctible locking of digit; 3-passively correctible locking; 4-fixed deformity (15). Patients will complete the quickDASH and EQ-5D questionnaires as well as a pain visual analog scale at each follow-up visit (27).
- 2) De Quervain's tenosynovitis group primary endpoint measures will include objective physical exam findings for the resolution of pain/tenderness over the 1st dorsal extensor compartment and the resolution of pain elicited during the Finkelstein test. In addition, patients will complete the quickDASH and EQ-5D questionnaires as well as a pain visual analog scale at each follow-up visit.
- 3) Lateral epicondylitis of the elbow group primary endpoint measures include the resolution of lateral elbow pain/tenderness over the extensor origin and the resolution of pain at the lateral epicondyle with resisted wrist extension during follow-up examinations. Patient grip strength will also be measured in this cohort using a hand dynamometer. Grip strength will be measured at each follow-up and the average of three tests with 20 second rests in between will be recorded. The contralateral side will also be measured for comparison. Lastly, patients will complete the quickDASH and EQ-5D questionnaires as well as a pain visual analog scale at each follow-up visit.

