4.4 Subject Withdrawal

Patients can withdraw from the study at any time if they wish. Patients whose symptoms do not improve and are candidates for surgery can withdraw from the study and have surgery to correct their specific pathology (secondary endpoint). Patients enrolled in the study will be counseled regarding the likelihood of the injections working and will be given the opportunity for a second injection at 4 weeks from the time of the first injection if no significant symptoms have resolved. Ultimately it will be up to the patient whether they chose another injection or if they want to resort to a surgical intervention.

If patients experience adverse events they will be counseled regarding treatment alternatives for their pathology and any complications from the injection/medications will be treated appropriately. Because the study consists of a single injection at time point zero followed by serial examinations and completion of functional outcome surveys there is no need to stop treatment and withdraw patients from the study despite having an adverse event. The patient will simply not receive any more injections.

5 Study Drugs

5.1 **Ketorolac** (Investigational Agent)

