7.2 Statistical Methods

Statistics will be conducted by the statistician on faculty with the NYU Hospital for Joint Diseases. Primary analysis will consist of comparisons of the baseline functional scores (quickDASH and EQ5D). These scores will be analyzed and compared to subsequent scores at the various follow-ups (4-weeks, 8-weeks,

12-weeks, 6 months). In addition, changes in scores will also be analyzed between the baseline scores and the subsequent follow-ups. Statistical significance will be determined by p-values less than 0.05.

Secondary analysis will consist of physical exam findings and resolution of symptoms following injections as well as grip or pinch strength using pressure dynamometers to gage improved function following injections as well. In addition, observation of side effects will also be included in the secondary analysis.

8 Safety and Adverse Events

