10.1 Study Monitoring

For full details on study data and safety monitoring, see the accompanying Data and Safety Monitoring Plan for this study. The responsibility for gathering the data will rest with the individual investigators/health care providers that are directly treating the patients (either at the NYU HJD hand clinic on 23rd street or in the private office of hand attending). Individuals treating patients will be informed to relay any unanticipated problems/concerns/adverse events to the resident research coordinator ([name]). Data will be consolidated and sent to the resident researcher for further evaluation and for monitoring during the course of each patient's length of treatment.

The resident research coordinator ([name]) will ensure data accuracy by monthly asking how the data was collected and ensuring individuals are following proper protocol. In addition, data accuracy will also be maintained with quick training sessions on the study to be conducted at the study site once every 2 month basis. This will be done by the hand research coordinators/assistants, the resident researchers, or the principal investigators/attending involved. Monitoring work will be reviewed at regular intervals with the study Principal Investigator.

Patients that ultimately drop out of the study will be monitored for the course of their regularly scheduled follow-up appointments until there are discharged from the clinic or the care of the attending orthopaedic hand surgeon.

Primary and secondary efficacy endpoints will be monitored. Either patients will have resolution of their symptoms (primary endpoint) with improvement in hand function to their desired satisfaction or they must undergo surgery (secondary endpoint) for correction due to failure of the local soft tissue injection in relieving their symptoms.

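### Sections 1.6.1 and 4.4 give incompatible rules after an adverse event; 4.4 probably governs, but following 1.6.1 could cost up to 8 primary-analysis scores per affected patient

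*Combined protocol and SAP*

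**What the plan says.** Two current statements in the combined protocol and SAP say what happens to a patient after an adverse event.

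- Section 1.6.1, in the paragraph on protection against risks: "Any patient that experiences an adverse event will be withdrawn from the study and will follow-up with their primary care provider promptly".
- Section 4.4, on subject withdrawal: "there is no need to stop treatment and withdraw patients from the study despite having an adverse event". The reason offered is that "the study consists of a single injection at time point zero followed by serial examinations and completion of functional outcome surveys", and the stated consequence is: "The patient will simply not receive any more injections".

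The surrounding text matters for the consequences.

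- Section 8.1 defines an adverse event broadly. Any new or worsening symptom, sign or illness counts, intercurrent illness is included, and there is no threshold of severity or relatedness.
- Section 3.4 places follow-up at 4, 8 and 12 weeks and 6 months. Section 3.2 says of the trigger finger group, and in similar terms of the other two diagnoses: "Patients will complete the quickDASH and EQ-5D questionnaires as well as a pain visual analog scale at each follow-up visit".
- Section 7.2 builds the primary analysis on quickDASH and EQ-5D: "These scores will be analyzed and compared to subsequent scores at the various follow-ups". It names neither a missing-data method nor an analysis population.
- Section 10.1 has a central contact for safety reports: "Individuals treating patients will be informed to relay any unanticipated problems/concerns/adverse events to the resident research coordinator". That coordinator "will ensure data accuracy by monthly asking how the data was collected and ensuring individuals are following proper protocol". The section also says that drop-outs continue to be monitored at their usual appointments until discharge.
- Sections 8.4 and 10.1 refer to a Data and Safety Monitoring Plan, which was not among the documents available for this review.

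**The concern.** One section requires withdrawal from the study; the other keeps the patient in and stops only the injections. Whatever staff do after an adverse event departs from one of them. Section 8.2.1 asks for deviations that could recur to be reported to the IRB within 5 working days, so staff need to know which rule counts.

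The statistical stake is follow-up after randomisation. Withdrawal under 1.6.1 is triggered by something that happens after treatment. If outcome collection stops at that point, the patients left in the section 7.2 comparison are selected by a post-treatment event, and the plan has no stated method for handling the gap. Read literally, the 8.1 definition even includes worsening of the treated hand or elbow condition, so leaving the study could depend on the outcome being measured.

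**Working it through.** No figure in the plan bears on this point: it gives no adverse-event rate and no expected number of withdrawals for adverse events. The check is therefore a comparison of the text, plus a count of the scores at stake per patient.

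**1. Can the two rules be reconciled?** Section 4.4 says there is no need to withdraw, which alone is softer than a prohibition. Its closing sentence, however, fixes the consequence as an end to injections and nothing more. Section 1.6.1 applies to every patient with an adverse event and is mandatory. The two cannot both be carried out for one patient.

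**2. Does anything set precedence?** Neither section refers to the other, and no other section ranks them. Section 4.4 is the section on withdrawal and explains itself; 1.6.1 is background on risk. That favours 4.4 as the rule staff would use, but this is an inference.

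**3. How many patients could 1.6.1 reach?** Under the 8.1 definition, potentially many. Read as drug side effects only, which its setting suggests, it reaches fewer. Even then it would include injection-site pain, which 1.6.1 lists for both drugs.

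**4. What is at stake per withdrawn patient?** The inputs are the 2 instruments named in section 7.2 (quickDASH and EQ-5D) and the 4 follow-up visits in section 3.4. Scores lost = 2 × visits remaining.

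| Rule followed | Patient withdrawn before | Visits remaining | Primary-analysis scores lost |
|---|---|---|---|
| 4.4 | not withdrawn | – | 0 |
| 1.6.1, scores stop | week 4 | 4 | 2 × 4 = 8 |
| 1.6.1, scores stop | week 8 | 3 | 2 × 3 = 6 |
| 1.6.1, scores stop | week 12 | 2 | 2 × 2 = 4 |
| 1.6.1, scores stop | 6 months | 1 | 2 × 1 = 2 |

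These are maxima. Section 1.6.1 has side effects checked at the follow-up visits, where the questionnaires are also completed, so an event first found at a visit need not cost that visit's scores. Losing all 8 requires the patient to report the event and be withdrawn before week 4.

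**5. Are the scores secured elsewhere?** Section 10.1 promises monitoring of drop-outs but does not say that quickDASH or EQ-5D will still be collected or analysed. Section 9.3 asks for missing data to be explained, which is not the same as collecting it. The monthly check by the coordinator is against the protocol, and the protocol gives two answers.

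**6. Would the loss differ by drug?** Section 1.6.1 lists partly different risks for dexamethasone and ketorolac, so it could. But both groups receive the same lidocaine dose (sections 5.1.2, 5.2.2 and 5.3) and share its listed risks. Section 1.6.1 also says that the ketorolac risks come mainly from systemic or intramuscular use and that none are noted for local soft-tissue injection. Section 1.1 says most systemic NSAID effects should in theory be avoided by local injection. A list of risks is not a rate, and no rates are given.

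**The case against.** The strongest reply is that this is a drafting slip with no practical effect. Section 4.4 is where staff would look, it gives its reason, and following it loses nothing. Adverse events go to a coordinator who checks adherence monthly, drop-outs are still monitored, section 8.3 expects a low side-effect profile, and the monitoring plan may already settle the matter. Harm would need staff to follow the background section, the questionnaires to stop, and, for a biased drug comparison, the affected patients to differ between groups in number or outcome.

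Most of that stands, and it limits the point to a conditional one. It does not remove a mandatory sentence from the protocol or supply the missing commitment to collect scores. If the monitoring plan does settle the matter, 1.6.1 would still need correcting.

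A reader might infer three stronger things that the documents do not support:

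- *That outcome data will be lost selectively by drug.* Step 6 of the working shows this is possible but not demonstrated.
- *That 12 scores per patient are at risk to the primary analysis.* This adds the pain scale, which section 3.2 schedules but section 7.2 does not name.
- *That power falls by a stated amount, or the drug difference is biased by a stated number of points.* Any such figure would need assumed event rates and assumed outcomes for withdrawn patients. Section 7.1 also already allows 30% for loss to follow-up, without saying whether these withdrawals fall inside it.

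It can fairly be added that 4.4 rests on the same broad notion of adverse event when it stops injections, so expected soreness could deny someone the second injection. That affects treatment received, not whether outcomes are collected.

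**Conclusion.** The contradiction is real and can be seen from the two sections alone. Section 4.4 is probably the operative rule, and if it is followed the loss is zero. If 1.6.1 is followed and questionnaires stop, patients are removed after randomisation for a broadly defined post-treatment event, at a cost of up to 8 primary-analysis scores each (6, 4 or 2 for later withdrawals).

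The effect on the trial as a whole is unknown and may be small. Confidence is high that the rules conflict, moderate that staff would follow 4.4, and low on the size of any effect. The conclusion assumes that neither the Data and Safety Monitoring Plan nor the consent form, neither of which was available, already states a governing rule. The correction is worth making because it is easy and closes an avoidable route to post-randomisation loss.

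**What to change.** - **Section 1.6.1:** delete the clause that withdraws the patient from the study. The sentence then says only that a patient with an adverse event follows up promptly with the primary care provider.
- **Section 4.4:** make this the single rule. After an adverse event the patient receives no more injections, stays in the study, and completes the remaining scheduled visits and questionnaires unless consent is withdrawn. State that those scores are analysed in the randomised group.
- **Related documents:** check that the Data and Safety Monitoring Plan and the consent form carry the same rule.

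The cost is a wording amendment and that consistency check. The visits and questionnaires are already scheduled, so no added visits, staff or patients are needed.

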8.1 Definitions

Adverse Event

An **adverse event** (AE) is any symptom, sign, illness or experience that develops or worsens in severity during the course of the study. Intercurrent illnesses or injuries should be regarded as adverse events. Abnormal results of diagnostic procedures are considered to be adverse events if the abnormality:

- results in study withdrawal
- · is associated with a serious adverse event
- is associated with clinical signs or symptoms
- leads to additional treatment or to further diagnostic tests
- is considered by the investigator to be of clinical significance

Serious Adverse Event

Adverse events are classified as serious or non-serious. A serious adverse event is any AE that is:

- fatal
- life-threatening
- requires or prolongs hospital stay
- · results in persistent or significant disability or incapacity
- a congenital anomaly or birth defect
- an important medical event

Important medical events are those that may not be immediately life threatening, but are clearly of major clinical significance. They may jeopardize the subject, and may require intervention to prevent one of the other serious outcomes noted above. For example, drug overdose or abuse, a seizure that did not result in in-patient hospitalization, or intensive treatment of bronchospasm in an emergency department would typically be considered serious.

Recording of Adverse Events

At each contact with the subject, information will be sought from each subject on adverse events by specific questioning and, as appropriate, by examination. Information on all adverse events should be recorded immediately in the source document, and also in the appropriate adverse event module of the case report form (CRF). All clearly related signs, symptoms, and abnormal diagnostic procedures results should recorded in the source document, though should be grouped under one diagnosis.

All adverse events occurring during the study period must be recorded. The clinical course of each event should be followed until resolution, stabilization, or until it has been determined that the study treatment or participation is not the cause. Serious adverse events that are still ongoing at the end of the study period must be followed up to determine the final outcome. Any serious adverse event that occurs after the study period and is considered to be possibly related to the study treatment or study participation should be recorded and reported immediately.

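### Sections 1.6.1 and 4.4 give opposite rules for a patient with an adverse event: the first withdraws the patient from the study, the second keeps the patient in follow-up without further injections.

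*Combined protocol and SAP*

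**What the plan says.** Two sections of the combined protocol and SAP tell staff what to do with a patient who has an adverse event.

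- Section 1.6.1 (Risk of Study Drug), in the paragraph on protection against risks: "Any patient that experiences an adverse event will be withdrawn from the study". The same sentence sends the patient to a primary care provider.
- Section 4.4 (Subject Withdrawal): "there is no need to stop treatment and withdraw patients from the study despite having an adverse event". The reason given is that treatment is one injection at the start, after which only examinations and questionnaires remain. The consequence is stated next: "The patient will simply not receive any more injections".

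Three other sections touch on the point. Section 8.1 defines an adverse event and requires each one to be followed until it settles or the study is ruled out as its cause. Section 10.1 says: "Patients that ultimately drop out of the study will be monitored for the course of their regularly scheduled follow-up appointments", until discharge from care. Section 9.3 requires missing data to be explained. None of these says whether 1.6.1 or 4.4 applies.

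**The concern.** Patients are treated in private offices and a resident clinic (4.3). Two physicians who each follow the protocol could handle the same event differently: one ends participation, the other continues the visits.

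The choice affects the main data. Section 7.2 makes quickDASH and EQ-5D at 4, 8 and 12 weeks and 6 months, set against baseline, the primary analysis. Withdrawal under 1.6.1 happens after randomization and depends on what happened after the injection. If events are more frequent with one drug, or of a different kind, and the patients who leave would have scored differently from those who stay, the patients left in the two groups are no longer comparable in the way randomization made them. Withdrawal would also shorten in-study observation of the patients whose safety matters most, including those given ketorolac outside its approved indication.

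**Working it through.** The plan states no figure on this point, so the check is a comparison of the texts.

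**1. Is the trigger the same?** Yes. Both sections speak of a patient who has an adverse event, and neither limits this by seriousness or relatedness.

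**2. Is the instruction the same?** No.

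| | 1.6.1 | 4.4 |
|---|---|---|
| Study participation | ends (mandatory wording) | continues |
| Further injections | none, because participation ends | none |
| Later questionnaires | not provided for | continue as part of follow-up |
| Primary-care referral | yes, promptly | not mentioned; alternatives are discussed and complications treated |

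The sections agree that no more injections are given. They conflict on whether the patient stays in the study.

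**3. Can the two be read together?** Suppose 4.4 only permits the patient to stay. Then 1.6.1 still forbids it. Suppose instead that 1.6.1 covers only reactions to the injection. Then 4.4 still keeps those same patients in. Neither reading removes the conflict.

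**4. Does another section decide it?**
- 8.1 secures follow-up of the event itself, not the questionnaires.
- 10.1 secures clinical monitoring of patients who drop out. It does not say that quickDASH or EQ-5D is still collected or analysed.
- 9.3 asks that missing data be explained, which does not recover them.
- 1.6.1, 8.4 and 10.1 refer to a Data and Safety Monitoring Plan, which is not available here.

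**5. What differs for one patient?** Take a skin rash, a listed ketorolac risk in 1.6.1, reported at the 4-week visit after that visit's scores are taken. Four post-injection assessments are scheduled. Under 1.6.1 the remaining 4 − 1 = 3 (8 weeks, 12 weeks, 6 months) are no longer provided for. Under 4.4 all three go ahead.

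**6. How many patients?** The number withdrawn per diagnosis would be 260 × the proportion with an adverse event. The documents give no such proportion, overall or by drug, so neither the loss nor the bias can be calculated. Section 1.6.1 does list different risks for the two drugs (for example fat atrophy and pigment change against rash and gastrointestinal effects). Unequal withdrawal is therefore plausible but not shown.

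**The case against.** The strongest reply is that the intended rule can be guessed. Section 4.4 is the section devoted to withdrawal and gives a reason for its rule, whereas 1.6.1 is one sentence in the introduction. A careful reader would probably follow 4.4, and then no scores are lost. This stands in part: the harm is conditional on 1.6.1 being applied. It does not remove the conflict, because no text gives 4.4 precedence and the 1.6.1 wording is mandatory.

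A second reply is that 8.1, 9.3 and 10.1 protect withdrawn patients. They do protect clinical care and follow-up of the event, and they should be credited for that. They do not secure the outcome scores.

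Three stronger readings are tempting, and the documents do not support them.

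- *That 1.6.1 removes everyone with an unrelated illness or a worsening of the treated condition.* This needs the 8.1 definition, under which an adverse event "is any symptom, sign, illness or experience that develops or worsens in severity during the course of the study", to be carried into a paragraph about drug risks. There the term may well mean a reaction to the injection. Poor response also has its own route in 4.4 (a second injection or surgery).
- *That the trial loses a stated amount of power.* Enrolling 260 = 200 × 1.3 and losing 30% leaves 260 × 0.70 = 182, below the 200 in 7.1. That shortfall is there with no adverse events at all. It is a separate matter and does not measure this one.
- *That the bar on re-injection in 4.4 is also an error, because it is not limited to related events.* Withholding an optional second injection after any adverse event is a defensible, cautious rule. Loosening it is a trade-off, not a correction.

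**Conclusion.** The contradiction is certain: it is on the face of two current sections and requires no inference. Its consequence is conditional. If 1.6.1 is applied, primary-analysis scores and in-study safety follow-up may be lost for patients with adverse events, and the drug comparison can be biased if events differ by drug. If 4.4 is applied, this loss does not occur. No size can be given without an adverse event rate. The conclusion assumes that the Data and Safety Monitoring Plan does not settle the matter. Even if it does, the protocol would still carry two opposite instructions and should be corrected. The change should be made: the text is wrong as written, and the remedy is the protocol's own rule in 4.4.

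**What to change.** In 1.6.1, replace the withdrawal wording with the rule of 4.4. Suggested text: *A patient who has an adverse event receives no further study injections, sees the primary care provider promptly, and continues the scheduled visits with quickDASH, EQ-5D and pain scale through 6 months, unless the patient chooses to withdraw.* Check that the Data and Safety Monitoring Plan says the same.

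The cost is an edit to one sentence. No visits are added, because the schedule already runs to 6 months. Section 4.4, the adverse event definition in 8.1 and the patient's right to leave at any time stay as they are.
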